**A.8.4. Provide a compelling justification for the proposed sample size in terms of the likelihood of achieving each aim.**

Over the course of the study period, there will be a finite number of possible enrolled subjects. We expect to enroll a total target sample size of  $N = 80$  eligible subjects. Our funding will provide for 40 patients to undergo the new treatment plan with 40 standard dressing subjects as a comparison. We anticipate that about 10 subjects will have incomplete data due to compliance, drop-out, and other causes. This will result in a recruitment of up to 90 subjects in order to result in 80 subjects completing the trial.

Our primary goal is to test the difference between two independent groups at a specific time point (namely, one week post op). We can think of this as a two independent groups t-test. With  $n_1=40$  vs  $n_2=40$ , we will have 80% power to reject the null if the difference between the means of the two conditions were 0.63 standard deviations apart (and with greater power if the differences were bigger). Any difference of less than 0.63 SDs would be seen as not clinically significant. Small differences in the score of 1-2 points would fall within this and can be attributed to observer differences and would likely not be sensitive for detecting any risk for surgical infection.

The experimental dressing is expected to have benefit by reducing wound healing characteristics related to complications (ASEPSIS score) and subsequently reducing postoperative infections. There is an extremely low rate of infections in primary total hip arthroplasty surgeries and infection cannot be measured with this limited population (0.5% to 3.0% of the population). Adverse secondary events also have a low incidence and our study is not designed or powered to identify a statistically significant difference in these events, although such events will be recorded and examined for exploratory purposes. The ASEPSIS score allows a lower sample size that is within our reach to detect changes and will be used to identify infection risk.

In summary, the proposed target sample size was based on the number of enrollable subjects we believe we would plausibly have access to, based on the availability of eligible subjects, conjectures about the feasible rate of recruitment, and the length of time available to conduct the study. A sensitivity-type power analysis shows that our sample size will have adequate power (80%) to detect a clinically meaningful improvement (.63 SDs) in the ASEPSIS score, which is intrinsically beneficial and a predictor of more serious adverse outcomes.

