### A.8. Data analysis

#### A.8.1. Summarize the statistical analysis strategy for each specific aim.

Our primary goal is to test the difference between two independent groups at one week post op. Our feasible total sample size is 80 subjects. The progression of the ASEPSIS score over the six week post op recovery period will not be rectilinear. All patients are expected to be infection free with very low ASEPSIS scores immediately following the operation and are likely to be fully healed at six weeks. Attempting to model the timecourse of the ASEPSIS score with splines or multiple dummy variables and including all potential covariates would require considerable degrees of freedom and model tweaking based on intermediate assessments of model fit. Such a model would likely be too saturated to yield meaningfully narrow standard errors and holds considerable danger for overfitting. This modeling process does have some value for exploratory purposes, and we will employ it as such, but it will not be appropriate for confirmatory hypothesis testing. Instead, we note that the timepoint when differences in wound healing are most pronounced is after one week. Because subjects will be randomized to the two arms, we can consider the relevant population to be balanced on their covariates. The null hypothesis is simply that the treatments do not differ in ASEPSIS score at one week post op. Thus, we have a two independent groups t-test as a valid test

of our a-priori hypothesis.

A biostatistician ([name], NC TRACS) has been recruited and will provide the statistical computations and interpretive analyses required for the exploratory model-based analyses of the data. Estimates of effect magnitude, confidence intervals and sensitivity analyses will augment the exploratory modeling that will be conducted.

**A.8.2. What are the practical objectives of the study? Examples: pilot study to obtain data for a grant proposal, train junior investigators, create a registry, develop new assay methods, pilot-test procedures, evaluate feasibility, generate hypotheses, estimate parameters, test hypotheses.**

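### A.8.4 presents 0.63 SD, the effect that a feasibility-based 40 per arm can detect, as the limit of clinical significance, with no SD or threshold in ASEPSIS points to support it

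*Combined protocol and SAP*

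**What the plan says.** A.8.4 is open about where the sample size comes from: "the proposed target sample size was based on the number of enrollable subjects we believe we would plausibly have access to". Funding covers 40 patients on the new dressing, with 40 on the standard dressing as comparison. For a two-group t-test at one week it then reports "80% power to reject the null if the difference between the means of the two conditions were 0.63 standard deviations apart".

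The next sentence gives that figure a second role: "Any difference of less than 0.63 SDs would be seen as not clinically significant". The reason offered is "Small differences in the score of 1-2 points would fall within this and can be attributed to observer differences", with the addition that such differences would probably not be sensitive to infection risk. The closing summary of A.8.4 claims "adequate power (80%) to detect a clinically meaningful improvement (.63 SDs) in the ASEPSIS score".

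Alpha and sidedness are not stated. No SD or expected mean of the one-week ASEPSIS score is given in points. The background (A.1.1, ASEPSIS Scoring System) does give two figures in points, a coefficient of repeatability of 4.1 and a cut-off above 20. A.8.4 uses neither.

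On the analysis, A.8.1 concludes "Thus, we have a two independent groups t-test as a valid test" and reasons "Because subjects will be randomized to the two arms, we can consider the relevant population to be balanced on their covariates". Estimation is attached elsewhere: "Estimates of effect magnitude, confidence intervals and sensitivity analyses will augment the exploratory modeling".

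Two sections decide whose one-week score is analysed. A.4.3 (Protocol Departures) keeps departures under evaluation for intention-to-treat analysis, but also allows a case-by-case decision to drop a patient. A.7.3 says that patients whose complications need more treatment are withdrawn from the study.

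**The concern.** A detectable difference answers the question of what this many patients can show. A clinical threshold answers what difference would matter to a patient or surgeon, and must not depend on how many patients a clinic can enrol. A.8.4 uses one number for both. By its wording, results of 0.63 SD or more may be called clinically meaningful and smaller ones unimportant, on a basis that is only the enrolment figure. With no SD and no threshold in points, a reader cannot check either statement.

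The confirmatory analysis adds to the problem. It promises a test but no estimate or interval, so nothing in it would show which effect sizes remain plausible. Also, if patients with early wound complications leave the data, some of the highest scores leave with them, because antibiotic treatment and operative debridement each add 10 points and local debridement adds 5.

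**Working it through.** **Inputs.** 40 per arm, 80% power, 0.63 SD and an unpaired t-test (A.8.4); 1:1 allocation (A.4.3); a null of no difference at one week (A.8.1). Assumed: two-sided alpha 0.05.

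**1. Reproducing the plan's figure.** Normal approximation: (1.960 + 0.842) × √(2/40) = 0.626 SD. Noncentral t with 78 degrees of freedom: 0.634 SD. Power at exactly 0.63 SD is 80.4% (normal) or 79.5% (t). The plan's figure is right. A one-sided 0.05 test would detect 0.56 SD, so two-sided 0.05 is the reading that fits.

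**2. Does the number depend on anything but enrolment?** Same t-test calculation, 80% power:

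| n per arm | detectable difference (SD) |
|---|---|
| 30 | 0.736 |
| 35 | 0.679 |
| 40 | 0.634 |
| 45 | 0.597 |
| 50 | 0.566 |

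At fixed alpha and power it depends on n alone. Had funding covered 30 or 50 per arm, the same reasoning would have given a different limit of clinical significance.

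**3. Does the 1-2 point remark support it?** For 2 points to lie within 0.63 SD, the SD must be at least 2/0.63 = 3.17 points. The documents give no SD, so a range is shown:

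| assumed SD (points) | 0.63 SD in points |
|---|---|
| 2 | 1.3 |
| 3 | 1.9 |
| 4 | 2.5 |
| 5 | 3.2 |
| 6 | 3.8 |
| 8 | 5.0 |
| 10 | 6.3 |

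The repeatability coefficient of 4.1 points equals 0.63 SD only if the SD is 4.1/0.63 = 6.5. Even where the remark holds, it shows that 1-2 points is small, not that everything below 0.63 SD is. It also takes observer variation in single scores as a yardstick for a difference between two group means.

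**4. Where the test and the limit part.** The test rejects once the observed difference reaches 1.991 × √(2/40) = 0.445 SD. Observed differences from 0.445 to 0.63 SD are therefore significant but below the stated limit. At an SD of 3.17 that band runs from 0.445 × 3.17 = 1.41 points to 2.0 points.

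**5. Covariate adjustment.** Simulation with a normal outcome, two covariates and a true difference of 0.63 SD gives power of 80.3%, 82.2% and 84.6% if the covariates explain 5%, 10% and 15% of the variance (assumed values), against about 79.5% unadjusted. If they explain nothing, power is 78.5%.

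**6. Withdrawals.** Losing one wound that scores 10 points above the rest of its arm of 40 moves that arm's mean by 10/40 = 0.25 points, or 0.25/3.17 = 0.08 SD at the smallest SD that fits the plan's remark.

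**The case against.** The plan does offer a rationale, so it would be wrong to say that the limit has no clinical basis at all. It treats 1-2 points as observer difference and of little value for infection risk. That stands as an informal statement, but it is uncited and does not lead to 0.63 SD.

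A reader might infer that a significant result between 0.445 and 0.63 SD will be dismissed. The documents do not establish this. The sentence sits in a sample-size justification, A.8.1 contains no decision rule that uses 0.63 SD, and nothing says whether the limit refers to the observed or the true difference. Nor is the existence of such a band a fault: any trial with 80% power at its target effect has one, and at a true 0.63 SD it holds about 29% of results here.

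The plan also says plainly that the sample size came from feasibility and calls its calculation sensitivity-type. Correcting the label changes neither the sample size nor the p-value.

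On adjustment, the unadjusted t-test is valid under randomisation. The documents name obesity as an infection risk factor but give no specific reason to choose age. The gain rests on assumed explained variance and a normal outcome, so this is an improvement and not a correction. The overfitting worry in A.8.1, however, concerns time-course models with every potential covariate, not two prespecified ones.

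On withdrawals, a patient withdrawn after the one-week visit already has the primary score, and A.4.3 says that departures continue to be evaluated. Only events before that visit can remove a score, and one lost wound moves the mean little. The two sections still conflict for those patients.

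**Conclusion.** The concern holds as a fault of interpretation. A.8.4 reuses a number that follows from 40 per arm as the limit of clinical significance. The number would be 0.74 SD with 30 per arm and 0.57 SD with 50, and its only stated support cannot be converted without an SD that the documents do not give.

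It might be inferred that the power calculation or the primary test is wrong. Neither is: 40 per arm gives about 80% power at 0.63 SD, assuming two-sided alpha 0.05, and the t-test stands. What cannot be judged is whether 0.63 SD matters clinically, or how many points it is. Power falls to about 60% for a true 0.5 SD and 42% for 0.4 SD, so a non-significant result should not be read as excluding effects of that size.

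Confidence is high for the threshold and the missing interval. The covariate and withdrawal items are secondary, and their size depends on assumptions.

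**What to change.** 1. **A.8.4.** Delete the sentence "Any difference of less than 0.63 SDs would be seen as not clinically significant". In the closing summary, describe 0.63 SD as the detectable difference and not as clinically meaningful. State two-sided alpha 0.05. If a clinical threshold is wanted, give it in ASEPSIS points with a rationale that does not depend on the sample size, together with an assumed SD and its source, or a range of SDs. The pilot testing in A.8.5 covers data management and project operation. It promises no scored wounds and should not be relied on for the SD.
2. **A.8.1.** Make the one-week mean difference in points, with its two-sided 95% confidence interval, part of the confirmatory analysis. Interpret it in both directions, so that a result favouring the standard dressing is reported as such.
3. **Secondary improvement.** Prespecify adjustment of the primary comparison for BMI and age. A.8.5 lists both as data to be collected, but Table 1a omits BMI, so add it there.
4. **A.4.3 and A.7.3.** Reconcile them so that one-week scores are still collected, and analysed as randomised, for patients whose event falls before that visit. This concerns data only. When to stop or change a dressing is not at issue here.

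**Cost.** Protocol wording and one table row, with no added patients or visits. The team must find a source or range for the SD and, if it wants a threshold, a rationale in points. Adjustment uses two degrees of freedom and loses about 1 point of power (79.5% to 78.5%) if BMI and age explain nothing.

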#### A.8.5. Summarize the plans for data management.

Management of the research data for this study will involve collection, entry, processing, storage, retrieval, archival, distribution and documentation of information collected according to a written protocol. The overall strategy for quality assurance in data management will be assisted by the use of REDCap software and the TraCS institute([name]).

REDCap and TraCS Research Management. The TraCS Clinical Research Data Management Service is a key initiative of the Biomedical Informatics core of the UNC-Chapel Hill CTSA. The purpose is to provide a system, and associated support resources, to enable efficient and high quality collection and management of research data that is standards-based in design, development and implementation. Standard features of electronic clinical research data management systems are available in the web-based systems provided with the service. These include interactive data entry with real-time field validation, lab data imports, audit logs to record database modifications, database integrity checks, security (in logins, permissions based on need, and encryption), reporting, forms inventory, and exports to common statistical packages for analysis.

The database system provides for secure web-based data entry with the data stored on servers that we maintain. The data is encrypted during transmission. The servers are located in a secure campus area with all the appropriate physical security measures in place. The web and database servers are monitored by the TraCS IT staff, patched frequently, and scanned by a third party vendor to ensure that they are protected against known vulnerabilities. The scanning application is the standard service for the entire campus. Access is by individual user id, and is restricted to the forms and/or functions that the user needs to have. The applications themselves are written using open source tools, and have also been scanned by campus security office to ensure that the applications also are protected from known exploits. The data is backed up to electronic media on a daily basis. The electronic media is secured by ITS stored in a secure area separate from the servers.

Quality Assurance. The P.I. will have overall responsibility for ensuring quality in the data and in the procedures that produce the data. The P. I. will have overall responsibility for the definition and production of the documents necessary to describe all aspects of the study in sufficient detail to insure the study can be conducted in a scientifically sound, standardized manner. The P.I. will be assisted by members of the research team in monitoring adherence to protocol.

Database Security. The database will be created within centralized files and maintained on University approved; password protected, encrypted, shared research drives in the orthopaedic surgery department and viewed only on approved devices by approved study personnel.

PHI Security. Procedures to maintain privacy and confidentiality will be followed rigorously. For each subject, identifying information and protected health information (PHI; e.g., demographic information, medical history, laboratory results, insurance information) will be collected along with scientific study data (e.g., treatment group assignment, medical chart data, responses to treatment). Each research subject will be assigned a study identification number (ID) and applied within REDCap. The scientific study data will be stored in a digital file that does not include patient identifiers or PHI. A separate data file will contain identifiers and PHI. A master file linking patient identifiers to the study data will be kept by the principal investigator. The database will be password protected and will be stored on servers housed in a secure location.

Confidentiality. Research data will be identified only by study identification numbers (IDs). These study IDs will be used to maintain relationships in the data between various tables. All consent forms and any paper data collection instruments will be stored in a locked cabinet in a secure location. The list identifying subjects with their contact information will be kept separate from the scientific study data.

Case Report Forms (CRFs). As it is not unusual for revisions to the CRFs to occur in clinical studies, each form will be clearly labeled with a set number. Transition to an updated version of a CRF will be communicated to all members of the research team.

**Data Collection.** Study data will be recorded at the point of care using data collection instruments provided by the study team. Paper forms will be stored in a designated folder securely maintained at the point of care and will be retrieved by the study team on a daily basis. The subjects' medical records will be reviewed to obtain study data and the patient characteristics at admission (e.g., age, sex, race, BMI). The medical record data will be recorded on a patient-specific CRF. Data collection will adhere to precise written instructions and will be monitored to insure adherence to the protocol.

**Data Entry.** All data entered into the database from the CRFs will be verified by comparing the original CRFs to the values in the database.

**Data Editing.** The P.I. will be responsible for reviewing data-monitoring results and investigating questions raised (i.e., "queries") about remarkable or questionable data values.

**Database Documentation.** The names of the variables and their valid ranges or categorical values will be listed in a "data book". Documentation will also include an index of computer programs and an index of reports. All programming for statistical computation will include comments providing internal documentation.

**Pilot Testing of Operations.** All aspects of data management and project operation will be pilot tested prior to the commencement of the study in order to verify adequacy of the methods, materials and systems prepared. Every clinical study collects such pilot data -either intentionally prior to commencement of the study, or unintentionally after recruitment has begun.

**Risk of Deductive Disclosure.** We will minimize the risk of unauthorized persons using the database to figure out a subject's identity and responses.

(1) The database will comprise two separate files: a TRACKING FILE (containing sensitive patient identifiers such as name, birthdate, date and time of admission to the ER, and Subject\_ID) and a de-identified RESEARCH FILE containing non-sensitive data such as Subject\_ID, age, treatment assignment, ASEPSIS data, etc. Both database files contain Study\_ID. This allows the two sets of information to be linked together if necessary, but prevents linkage as long as the two files are kept safely separated.

(2) The database will be secured on encrypted storage media to guard against hacking or other unauthorized access. Paper forms will be stored in locked locations.

(3) Data will be retrieved from the RESEARCH FILE and distributed to specific personnel (e.g., the P.I., or co-investigators) for purposes of statistical computations for preparation of publications. Storage, retrieval and distribution will be carefully and securely controlled. Digital transmission of the data will be encrypted. Transportation of the data will use secure media.

## A.9. Identifiers

A.9.1. Check which of the following identifiers you already have or will be receiving, or select "None of the above."

- Names (this would include names/signatures on consent forms)
- Telephone numbers
- Any elements of dates (other than year) for dates directly related to an individual, including birth date, admission date, discharge date, date of death. For ages over 89: all elements of dates (including year) indicative of such age, except that such ages and elements may be aggregated into a single category of age 90 and older

- Any geographic subdivisions smaller than a State, including street address, city, county, precinct, zip code and their equivalent geocodes (e.g. GPS coordinates), except for the initial three digits of a zip code
- Fax numbers
- Electronic mail addresses
- Social Security numbers
- Medical record numbers
- Health plan beneficiary numbers
- Account numbers
- Certificate/license numbers
- Vehicle identifiers and serial numbers (VIN), including license plate numbers
- Device identifiers and serial numbers (e.g., implanted medical device)
- Web universal resource locators (URLs)
- Internet protocol (IP) address numbers
- Biometric identifiers, including finger and voice prints
- Full face photographic images and any comparable images
- Any other unique identifying number, code, or characteristic, other than dummy identifiers that are not derived from actual identifiers and for which the re-identification key is maintained by the health care provider and not disclosed to the researcher
- None of the above

#### A.9.2. For any identifiers checked, how will these identifiers be stored in relationship to the research data?

- with the research data (i.e., in the same data set and/or physical location)
- separate from the research data (i.e., coded with a linkage file stored in a different physical location)

**Provide details about the option you selected above:**

(1) The database will comprise two separate files: a TRACKING FILE (containing sensitive patient identifiers such as name, birthdate, date and time of admission to the ER, and Subject\_ID) and a de-identified RESEARCH FILE containing non-sensitive data such as Subject\_ID, age, treatment assignment, ASEPSIS data, etc. Both database files contain Study\_ID. This allows the two sets of information to be linked together if necessary, but prevents linkage as long as the two files are kept safely separated. (2) The database will be secured on encrypted storage media to guard against hacking or other unauthorized access. Paper forms will be stored in locked locations. (3) Data will be retrieved from the RESEARCH FILE and distributed to specific personnel (e.g., the P.I., or co-investigators) for purposes of statistical computations for preparation of publications. Storage, retrieval and distribution will be carefully and securely controlled. Digital transmission of the data will be encrypted. Transportation of the data will use secure media.

A.9.3. Are you collecting Social Security Numbers to be used as a unique identifier for study tracking purposes for national registry or database? (Do not check yes if collecting SSN *only* for payment purposes; this will be addressed later.)

No

